6.2. Background Characteristics

6.2.1. Participant Disposition

The number and percentage of participants in the following categories will be summarized by treatment group as defined in [Section 6.1](#) based on Randomization Set:

- Full Analysis Set (FAS)
- Immunogenicity Subset
- Per Protocol Immunogenicity Subset (PPIS)

- PP Set for Immunogenicity –SARS-CoV-2 negative (PPIS-Neg)
- Safety Set

The percentage will be based on participants in the Randomization Set. A summary of reasons for participants who are in the Randomization Set but excluded from PPIS will also be provided. A listing of analysis sets will be provided based on the Randomization Set.

For screened failure participants, age (years), as well as sex, race, ethnicity, and reasons for screen failure will be presented in a listing.

The number and percentage of participants in each of the following disposition categories will be summarized by treatment group based on the Randomization Set:

- Received the dose of IMP
- Completed study
- Prematurely discontinued the study and the reason for discontinuation
 - Adverse Event
 - Death
 - Lost to follow-up (LTFU)
 - Physician decision
 - Pregnancy
 - Protocol deviation
 - Study terminated by sponsor
 - Withdrawal of consent by participant
 - Other

A participant disposition listing will be provided, including informed consent, participants who received injection, participants who completed study, participants who discontinued from participation in the study, with reasons for discontinuation.

In addition, randomized participants with any inclusion and exclusion criteria violation will also be provided in a listing.

Study duration will be summarized from the injection, until completed/discontinued the study or the data cutoff date, whichever occurs first, based on the Safety Set.

6.2.2. Demographics and Baseline Characteristics

Descriptive statistics will be calculated for the following continuous demographic and baseline characteristics: age (years), weight (kg), height (cm), body mass index (BMI) (kg/m^2). The number and percentage of participants will be provided for categorical variables such as age group (18 to <65, and ≥ 65 years), sex (female, male), race and race group (White, Black, Asian, other), ethnicity, baseline SARS-CoV-2 status (positive, negative), number of prior doses of COVID-19 vaccines (2, 3, 4, ≥ 5). Type of prior COVID-19 vaccine may be summarized if data warrants.

The summaries will be presented by treatment group as specified in [Section 6.1](#) based on Safety Set and PPIS.

6.2.3. Medical History

Medical history data will be coded by system organ class (SOC) and preferred term (PT) using the Medical Dictionary for Regulatory Activities (MedDRA). MedDRA version used for coding medical history diseases will be included in footnote of analysis output.

The number and percentage of participants with any medical history will be summarized by SOC and PT based on the Safety Set. A participant will be counted only once for multiple events within each SOC and PT. SOC will be displayed in internationally agreed order. PTs will be displayed in descending order of frequency in the ~~CCI~~ μg Investigational mRNA-1273.815 group and then alphabetically within SOC.

All medical history data will be presented in a listing.

6.2.4 Prior and Concomitant Medications

Prior and concomitant medications will be coded using the World Health Organization drug dictionary (WHODrug Global). WHODrug Global version used will be included in footnote of analysis output. The summary of concomitant medications will be based on the Safety Set, unless otherwise specified. Imputation rules for missing/partial dates of medications are detailed in [Appendix 4](#). Categorization of prior, concomitant and post medications are defined below:

- A medication taken before the study vaccine injection date is considered a “prior” medication;
- The medication taken on or after study vaccine injection date through end of study follow-up (approximately 2 weeks from study injection) will be considered as “concomitant” medication.

The number and percentage of participants using concomitant medications will be summarized by treatment groups as follows:

- Any concomitant medications throughout the study
- Any non-study vaccination throughout the study

A summary table of all medications that continued or newly received throughout the study will be provided by PT in descending frequency in the Investigational mRNA-1273.815 group.

Prior, concomitant medications will be presented in a listing.

Concomitant procedures will be presented in a listing only.

6.2.4. Study Exposure

Study IMP administration data including reasons for IMP injection not administered will be summarized in disposition table and presented in a listing.

6.2.5. Major Protocol Deviations

Major protocol deviations are a subset of protocol deviations that may significantly impact the completeness, accuracy, or reliability of the study data or that may significantly affect a participant’s rights, safety, or well-being. Major protocol deviations rules are developed based on the protocol and ongoing data and will be finalized before database lock.

The number and percentage of the participants with each major protocol deviation type will be provided by treatment group as defined in [Section 6.1](#) based on the Randomization Set.

Major PDs may impact immune response corresponding to the immunogenicity objective, and participants with such deviations will be excluded from the PPIS for immunogenicity analyses; these major PDs will be determined and documented by Sponsor prior to DBL and unblinding. Reasons of exclusion from the PPIS will be summarized and listed.

Major protocol deviations will be presented in a listing.

6.3. Immunogenicity Analysis

The analyses of immunogenicity will be based on the PPIS and will be by treatment group unless otherwise specified.

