8.2.7. Assessment for SARS-CoV-2 Infection

Study participants will have nasal swab samples collected for SARS-CoV-2 testing at timepoints specified in the SoA ([Section 1.3](#)).

Serum collected from all participants will be tested for bAb against SARS-CoV-2 nucleocapsid protein at Day 1.

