8.3.1.4. Adverse Event of Special Interest

An AESI is an AE (serious or nonserious) of scientific and medical concern specific to the Sponsor's product or program, for which ongoing monitoring and immediate notification by the Investigator to the Sponsor are required. Such events may require further investigation to characterize and understand them.

The Investigator's medical judgment must be applied to assess an event as an AESI, as most AESIs are based on medical concepts. [Table 4](#) does not provide a comprehensive list of terms.

[Table 4](#) describes events/medical concepts that are of interest in COVID-19 vaccine safety surveillance. Some are specific to vaccines; however, some are of interest due to their occurrence in the context of concurrent or recent COVID-19. Events falling into the descriptions below should be reported as AESIs, per-protocol, even when they occur during/following COVID infection.

Please note: COVID-19 itself is not an AESI.

Table 4: Adverse Events of Special Interest (COVID-19 Vaccines)

Medical Concept	Additional Notes
Anosmia, Ageusia	
 • New onset of anosmia or ageusia idiopathic etiology. • DOES NOT INCLUDE anosmia or ageusia associated with COVID-19, sinus/nasal congestion, congenital, or traumatic etiologies.
Subacute Thyroiditis	
 • Acute inflammatory disease of the thyroid (immune-mediated or idiopathic). • DOES NOT INCLUDE new onset of chronic thyroiditis.
Acute Pancreatitis	
 • New onset of pancreatitis in the absence of a clear, alternate etiology, such as alcohol, gallstones, trauma, recent invasive procedure, etc.
Appendicitis	
 • Any event of appendicitis.
Rhabdomyolysis	
 • New onset of rhabdomyolysis in the absence of a clear, alternate etiology, such as drug/alcohol abuse, excessive exercise, trauma, etc.
Acute Respiratory Distress Syndrome (ARDS)	
 • New onset of ARDS/respiratory failure due to acute inflammatory lung injury. • DOES NOT INCLUDE nonspecific symptoms of shortness of breath or dyspnea, nor events with underlying etiologies of heart failure or fluid overload.

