9.4. Statistical Analyses

The SAP will be developed and finalized before database lock and will describe the preplanned statistical analysis details/data derivations, the participant populations to be included in the analyses, and procedures for accounting for missing and/or unused data.

This section is a summary of the planned statistical analyses of the primary and secondary endpoints.

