4.1. Overall Design

This is a Phase 3b randomized, observer-blind, active-controlled, clinical study to assess descriptively the immunogenicity of an Investigational mRNA-1273.815 COVID-19 Vaccine compared to the licensed Spikevax vaccine, both containing the updated XBB1.5 strain, in previously vaccinated adults. Randomization will be stratified by age (18 to < 65 years, and ≥ 65 years).

The study comprises 3 scheduled in-clinic visits including a Screening Visit (Screening and dosing can be performed on the same day) per Protocol Section 1.2 and Protocol Section 1.3.

This study will be conducted in compliance with the protocol, GCP, and all applicable regulatory requirements.

In this multisite study, participants will be randomized to either licensed Spikevax or Investigational mRNA-1273.815 with a wider RNA encapsulation lower-limit specification. The percent RNA encapsulation lower-limit of the Investigational mRNA-1273.815 vaccine is no more than **CCI** lower than that of the licensed Spikevax vaccine, both of which target the Omicron subvariant XBB.1.5. The Investigator, study staff, study participants, study site monitors, and Sponsor personnel (or its designees) will be blinded to the IMP administered on Day 1 until study end.

With SARS-CoV-2 expected to circulating in the general population during the study, blood samples will be tested at baseline (preinjection Day 1) for the development of Ab directed against nonvaccine antigen (eg, Ab against the nucleocapsid protein), which will signify infection with SARS-CoV-2.

To assess the vaccine-induced immune responses, blood samples will also be collected from all participants on Day 1 (preinjection) and Day 15 for measurement of SARS-CoV-2 specific nAb responses.

In addition, participants will have nasal swab samples collected before the injection on Day 1 as well as on Day 15.

To monitor for safety, safety data will be collected and will include SAEs, and AESIs, and AEs leading to discontinuation from study participation.

Number of Participants:

Approximately 200 adult (≥ 18 years of age) participants will be enrolled and randomized (1:1) to licensed Spikevax or Investigational mRNA-1273.815.

Study Duration:

Participants will be in the study for approximately 2 weeks which includes 7 days for Screening (Day -7 to Day 1), 1 day of dosing (Day 1), and 2 weeks of follow-up.

Study Treatment:

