5.3. Immunogenicity Subset

Participants in the FAS who have immunogenicity testing.

5.4.Per-Protocol Immunogenicity Subset (PPIS)

The PP Immunogenicity Subset includes participants who received planned dose of study injection per schedule, complied with immunogenicity testing schedule (visit window in [Appendix 2](#)), and have no major protocol deviations that impact key or critical data. The PPIS will be the primary immunogenicity analysis set.

5.5.Per-Protocol Set for Immunogenicity –SARS-CoV-2 negative (PPIS-Neg)

Participants in the PPIS who have no serologic or virologic evidence of SARS-CoV-2 infection at baseline, i.e., who are SARS-CoV-2 negative, defined by both negative RT-PCR test for SARS-CoV-2 and negative serology test based on bAb specific to SARS-CoV-2 nucleocapsid.

5.6.Safety Set

All enrolled participants who received IMP. The Safety Set will be used for all analyses of safety. Participants will be analyzed according to the study treatment they actually received.

6. Statistical Analysis

6.1.General Considerations

The Schedule of Activities (SoA) is provided in the protocol Table 2.

General considerations for analyses will be applied to this study, unless otherwise specified. All analyses will be performed by treatment groups, unless otherwise specified. Statistical outputs (tables, figures, listings, and datasets) will refer to study participants as participants and will use vaccination, injection of IMP and injection interchangeably. All analyses will be conducted using SAS Version 9.4. All table data will have a corresponding listing.

For the summary statistics of all numerical variables unless otherwise specified, the display precision will follow programming standards. Please see [Appendix 1](#) for variable display standards.

When count data are presented, the percentage will be suppressed when the count is zero in order to draw attention to the non-zero counts. A row denoted “Missing” will be included in count tabulations where specified on the shells to account for dropouts and missing

values. The denominator for all percentages will be the number of participants in that vaccination group within the analysis set of interest, unless otherwise specified.

Continuous variables will be summarized using the following descriptive summary statistics: the number of participants (n), mean, standard deviation (SD), median, minimum (min), and maximum (max).

Categorical variables will be summarized using counts and percentages.

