6.4.1. Unsolicited Adverse Events

An AE is defined as any untoward medical occurrence associated with the use of a drug in humans whether it is considered drug related or not. SAEs, AESIs (defined in Protocol Table 4), and AEs leading to discontinuation of study participation will be collected throughout the study. All AEs started after the injection will be reported in summary tables.

Unsolicited AEs will be coded by SOC and PT according to MedDRA dictionary.

All summary tables for unsolicited AEs will be presented by SOC and PT for AEs with counts of participants included. Given study duration is approximately 2 weeks, the unsolicited AEs will be summarized throughout the study.

When summarizing the number and percentage of participants with an event, participants with multiple occurrences of the same AE or a continuing AE within SOC or PT group will be counted once. Separate listings for corresponding AE tables will also be provided.

In addition, adverse events based on CDC wording cased definition of pericarditis, myocarditis, and myopericarditis occurring after receipt of study vaccines (defined in Protocol Appendix 4) will be listed if data is available.

The number of events and number of participants with occurrences of selected AEs of clinical interests identified by SMQ throughout the study will be summarized for narrow scope, narrow and broad scope, separately.

6.4.1.1.AEs by System Organ Class and Preferred Term

The following summary tables of AEs throughout the study will be provided by MedDRA SOC and PT using frequency counts and percentages:

- All unsolicited AEs leading to discontinuation from participation in the study,
- All unsolicited AESIs.

6.4.1.2.Serious Adverse Events

The summary table of serious AEs throughout the study will be provided by SOC and PT using frequency counts and percentages.

Death events will be provided in a separate listing.

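### Does the SAP need a planned count, listing or analysis of the Day 15 SARS-CoV-2 swab?

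*SAP*

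**What the plan says.** Protocol 8.2.7 gives the purpose of the swabs: "Study participants will have nasal swab samples collected for SARS-CoV-2 testing at timepoints specified in the SoA". The Schedule of Activities marks them at Day 1 and Day 15, and SAP 4.1 repeats that "participants will have nasal swab samples collected before the injection on Day 1 as well as on Day 15". For serology, the same protocol section says "Serum collected from all participants will be tested for bAb against SARS-CoV-2 nucleocapsid protein at Day 1", so no anti-nucleocapsid test follows the injection.

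Footnote 4 of the Schedule of Activities names an assay and a use (RT-PCR, to detect virus) for the pre-injection swab only.

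The analysis uses infection status at baseline and nowhere else: baseline status (SAP 6.1), the negative per-protocol set PPIS-Neg (Protocol Table 5, SAP 5.5), the baseline summary (SAP 6.2.2) and one subgroup (SAP 6.3.2.3). On the analysis set, SAP 6.3 says "The analyses of immunogenicity will be based on the PPIS and will be by treatment group unless otherwise specified".

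Two general statements bear on the point. Protocol 9.4 says the SAP will cover "procedures for accounting for missing and/or unused data". SAP 6.1 says "All table data will have a corresponding listing".

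**The concern.** The Day 15 swab is the only scheduled infection result after injection, and it is taken at the visit that supplies the primary endpoint. An infection between Day 1 and Day 15 could raise the neutralising titre without any contribution from the vaccine. A reader comparing the arms could fairly ask how many participants were infected by then.

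The safety data would not answer. SAP 6.4.1 says "SAEs, AESIs (defined in Protocol Table 4), and AEs leading to discontinuation of study participation will be collected throughout the study", and Protocol 8.3.1.4 adds "Please note: COVID-19 itself is not an AESI". A mild or symptomless infection would therefore reach no safety table unless the participant withdrew because of it. The listing rule in SAP 6.1 follows tables, and no named table holds the Day 15 swab. Read strictly, the promise in Protocol 9.4 about unused data also looks unmet. At stake would be an unseen disturbance of the Day 15 geometric mean (GM), the GMR or the seroresponse rate (SRR).

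**Working it through.** **No plan figure to reproduce.** Neither document gives an infection rate, a titre SD or a basis for the sample size. The documents supply only 200 participants randomised 1:1 (Protocol 9.6, SAP 4.3), hence 100 per arm. All other inputs below are assumptions, and all 200 are taken as evaluable.

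**1. How many positives?** With proportion p positive on Day 15, the expected number is 200p and the chance of at least one is 1 − (1 − p)^200.

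| p (assumed) | Expected | P(at least one) |
|---|---|---|
| 0.1% | 0.2 | 18% |
| 0.5% | 1 | 63% |
| 1% | 2 | 87% |
| 2% | 4 | 98% |
| 4% | 8 | >99.9% |

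Whether some cases are likely depends on where the assumed range starts.

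**2. Effect on the GMR.** If infection multiplies the titre by f, and one arm of 100 has d more cases than the other, the difference in mean log titre moves by (d/100) × log f. The GMR is therefore multiplied by f^(d/100).

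| Excess d | f = 2 | f = 5 |
|---|---|---|
| 0 | 1.000 | 1.000 |
| 1 | 1.007 | 1.016 |
| 2 | 1.014 | 1.033 |
| 4 | 1.028 | 1.066 |

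An excess of 4 needs, for example, eight cases split 6 to 2.

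**3. Against the precision of the trial.** The 95% half-width on the log10 scale is t(0.975, 198) × SD × √(2/100), with t = 1.972.

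- SD 0.4: 1.972 × 0.4 × 0.1414 = 0.112, a factor of 1.29.
- SD 0.6: 1.972 × 0.6 × 0.1414 = 0.167, a factor of 1.47.

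The largest shift in the table is 0.04 × log10(5) = 0.0280. That is 25% of the half-width at SD 0.4 and 17% at SD 0.6. A harsher case, five excess cases with a 10-fold rise, gives 10^(0.05) = 1.12. Its log shift of 0.05 is 45% and 30% of the same half-widths.

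**4. Effect on the SRR.** One infected participant can change an arm's rate by at most 1/100, or 1 percentage point.

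**5. Would the swab identify the cases that matter?** Only in part. An infection first detected on Day 15 may be too recent to have raised the titre, so the multiplication in step 2 probably overstates its effect. An infection caught and cleared earlier may have raised the titre and is missed. Excluding Day 15 positives would also condition on a post-injection result.

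**6. Is Protocol 9.4 breached?** The sentence is general, and the section goes on to describe itself as a summary for the primary and secondary endpoints. The Day 15 swab belongs to none of these (Protocol Table 3, SAP 3). The SAP does contain rules on which data go unused: Appendix 2 selects among several assessments in a window, SAP 6.1 places unscheduled measurements, and SAP 6.2.1 and 6.2.5 report reasons for exclusion from the per-protocol immunogenicity set (PPIS).

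**7. Does silence in the SAP mean no listing?** No. SAP 6.1 leaves some display detail to table shells that are not in the documents, and Protocol 9.7.1 and SAP 6.5 both promise listings of individual data in the study report. Nor does the SAP name every listing: Protocol 9.4.2 promises one of pregnancy outcomes where data warrant, and the SAP never repeats it. The documents show only that no listing of this result is named.

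**The case for a change.** The strongest case for acting is that the remedy costs almost nothing. One small table and one listing, or a sentence saying the result is not used, would tell readers what every participant's second swab showed. Settling this before database lock and unblinding avoids a choice made after the data are seen. The general listing sentences do not commit anyone to a count by arm, and the anti-nucleocapsid test is not repeated.

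All of that is accurate. It supports a courtesy to the reader, but it does not identify a fault in the plan. A count by arm is a plain tabulation that can be made for the study report without any analytic choice. The one step that would involve a choice, a sensitivity analysis excluding positives, is the least informative, because the swab separates affected from unaffected titres poorly. The Schedule of Activities footnote also leaves open that confining infection status to baseline was deliberate, and no text states the assay for the Day 15 sample.

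**Conclusion.** No change is needed. The SAP indeed names no output for the Day 15 swab, but this is missing detail about a sample outside the objectives of a randomised, observer-blind, descriptive study without hypothesis tests. Protocol 9.4 is not clearly breached. Cases spread equally between arms leave the GMR unchanged under the simple model used here. Unequal cases shift it by 0.7% to 6.6% for an excess of 1 to 4 per 100 and a 2- to 5-fold rise, and by about 12% in the harsher case. Each of these shifts is less than half of the confidence interval's half-width on the log scale.

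These sizes rest on assumed infection rates, fold-rises and a log10 SD of 0.4 to 0.6. The conclusion depends little on the exact values, because the swab captures infections between Day 1 and Day 15 only in part, and the PPIS result would stay primary whatever it showed. If the Day 15 samples are tested, the analysts can list the results with the other individual data.

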6.3.1. Immunogenicity Assessments

Planned timepoints for all immunogenicity assessments are provided in the SoA (Protocol Section 1.3). The following analytes will be measured in blood samples for immunogenicity assessments:

- Serum nAb level against SARS-CoV-2 S protein as measured by pseudovirus and/or live virus neutralization assays

6.3.2. Analysis of Immunogenicity Endpoints

The geometric mean (GM) level will be calculated using the following formula:

$$10^{\left\{ \frac{\sum_{i=1}^n \log_{10}(t_i)}{n} \right\}}$$

where t_1, t_2, \dots, t_n are n observed immunogenicity levels.

The geometric mean fold-rise (GMFR) measures the changes in immunogenicity levels within participants. The GMFR will be calculated using the following formula:

$$10^{\left\{ \frac{\sum_{i=1}^n \log_{10}\left(\frac{v_{ij}}{v_{ik}}\right)}{n} \right\}} = 10^{\left\{ \frac{\sum_{i=1}^n \log_{10}(v_{ij}) - \log_{10}(v_{ik})}{n} \right\}}$$

where, for n participants, v_{ij} and v_{ik} are observed immunogenicity levels for participant i at time points j and k , $j \neq k$ and k is baseline.

For calculation of GM values, missing results will not be imputed. Values reported as below the LLOQ will be replaced by $0.5 \times \text{LLOQ}$. Values reported that are greater than the

ULOQ will be converted to the ULOQ if the numeric values are not available (i.e., if numerical values are available, the numerical values are used).

